**3.0. Research Plan:**

**3.1. Purpose:**

- 1) To randomize 450 participants to 1 of 3 arms: a) a gestational weight gain intervention (GWG-only); b) a postpartum weight loss intervention (PPWL-only), or c) a combined gestational weight gain and postpartum weight loss intervention (GWG+PPWL), and to determine the efficacy of the interventions on GWG as well as PPWL;
- 2) To identify the impact of the interventions on pregnancy-related medical outcomes and health care utilization (from the electronic medical record) and fitness test data (pregravid to 12-month postpartum, from the military fitness database);
- 3) To determine the impact of treatment engagement process data (e.g., session participation, self-monitoring, meal replacement adherence) on intervention outcome.

**3.2. Hypotheses, Research Questions or Objectives:**

Hypothesis 1: Participants randomized to GWG-only and GWG+PPWL arms will gain less weight during pregnancy than in those randomized to the PPWL-only arm.

Hypothesis 2: Participants randomized to the GWG+PPWL and PPWL-only arms will lose significantly more weight postpartum than those randomized to the GWG-only arm.

**4. Brief Summary of the study:**

We will determine the extent to which a GWG intervention, a PPWL intervention, or a combination of the two interventions are efficacious in improving healthy GWG, PPWL, military readiness and maternal/child health and reducing health care utilization. From the treatment engagement data, we will identify

potentially important mediators of the treatment outcome. These outcomes are expected to have an important positive impact because the intervention(s) could be disseminated to the entire U. S. Military and integrated into standard health care for pregnant/postpartum military women.

#### **5. Subjects:**

Study participants will be female, active duty military personnel stationed at Joint Base San Antonio.

#### **6. Inclusion/exclusion criteria:**

Inclusion:

- Participants will be female active duty military personnel and DoD beneficiaries (retirees and dependents), stationed at Joint Base San Antonio and at least 18 years old.
- Participants must be less than 12 weeks gestation upon recruitment (based on the date of their last menstrual period and confirmed by first trimester ultrasound at the first prenatal visit).
- Participants must be within the normal, overweight, or obese BMI ranges upon Baseline measurements.
- Participants must have at least 1.5 years left on their current duty assignment.

Exclusion:

- Participants who have any medical conditions that limit a participant's ability to engage in changes in dietary intake or increases in physical activity, based on the determination of physicians on the study team.
- Participants who have a high-risk pregnancy (i.e., Type I or II diabetes at conception or current multiple gestation), based on the determination of physicians on the study team.
- Participants who smoke at the time of conception (smoking cessation during pregnancy has significant benefits for fetal health, but the quitting process can be associated with weight gain and thus offers potential study confounds).

#### **7. Number of Subjects:**

TOTAL NUMBER OF SUBJECTS (nation-wide/study-wide): WHASC and SAMMC – 755 with 450 completing the study

**8. Use of an Investigational New Drug:** N/A

**9. Use of an Investigational Device:** N/A

**10. Use of a Placebo:** N/A

**PROTOCOL FOR CLINICAL INVESTIGATION – NON-EXEMPT HUMAN  
(Wilford Hall Ambulatory Surgical Center – WHASC)**

**2.3. The research relevance of this protocol focuses on:**

Diagnosis  Treatment  Medical Utilization/Managed Care  Prevention  Medical Readiness  
 Other

**2.4. Location(s):**

- a. Collaborating Facilities: WHASC and SAMMC
- b. Air Force Sites seeking Regional IRB: N/A
- c. List study sponsors: NIH

**3.0 Research Plan:**

**3.1. Purpose:**

- 1) To randomize 450 participants to 1 of 3 arms: a) a gestational weight gain intervention (GWG-only); b) a postpartum weight loss intervention (PPWL-only), or c) a combined gestational weight gain and postpartum weight loss intervention (GWG+PPWL), and to determine the efficacy of the interventions on GWG as well as PPWL;
- 2) To identify the impact of the interventions on pregnancy-related medical outcomes and health care utilization (from the electronic medical record) and fitness test data (pregravid to 12-month postpartum, from the military fitness database);
- 3) To determine the impact of treatment engagement process data (e.g., session participation, self-monitoring, meal replacement adherence) on intervention outcome.

**3.2. Hypotheses, Research Questions or Objectives:**

Hypothesis 1: Participants randomized to GWG-only and GWG+PPWL arms will gain less weight during pregnancy than in those randomized to the PPWL-only arm.

Hypothesis 2: Participants randomized to the GWG+PPWL and PPWL-only arms will lose significantly more weight postpartum than those randomized to the GWG-only arm

**3.3. Significance; 3.4. Military Relevance; & 3.5. Background and Review of Literature:**

Considerable attention has been given to the alarming prevalence of overweight and obesity in the U.S. population [1]. This epidemic extends to women of childbearing age [1], including women who are active duty personnel in the U.S. military and DoD TRICARE beneficiaries (retirees and dependents). As of 2011, 34% of active duty military women were overweight and 6% were obese [2]. Indeed, excess weight is

associated with \$1.1 billion dollars each year in medical costs in the military health care system [3]. Furthermore, specifically for active duty personnel, excess weight and inadequate fitness are frequent causes for discharge. The military must then recruit and train replacements for about \$50,000 per person, thus spending more than \$60 million a year due to failed first-term enlistees [3]. While the long-term impact of pregnancy on military fitness test performance is unknown, several studies have found that women have significantly lower fitness test scores at 6-months postpartum [4, 5]. Finally, pregravid overweight/obesity has been found to be a key risk factor for perinatal complications in both civilian [6] and military populations [7].

In addition to pregravid weight status, excessive gestational weight gain is another key risk factor for pregnancy and delivery complications (e.g., gestational diabetes, preeclampsia, caesarean delivery) [8-11] and negative health outcomes for infants [6, 10, 12] as well as overweight status later in life [11-14]. Excessive gestational weight gain is also associated with postpartum weight retention [15-19], a key concern for the U.S. military. Thus, gestational weight gain is a critical consideration, because it is a modifiable risk factor that can be addressed upon pregnancy confirmation.

Women are not meeting the Institute of Medicine guidelines for gestational weight gain. Recent research indicates that many pregnant women do not gain within the 2009 Institute of Medicine guidelines; specifically, 53-71% of normal weight women, 77-84% of overweight, and 74-83% of obese women exceeded the Institute of Medicine guidelines [20, 21]. Although there is limited research on excessive gestational weight gain among TRICARE beneficiaries, there is some indication that many active duty women, like the civilian population, are exceeding gestational weight gain guidelines [22].

Excessive gestational weight gain is a key predictor of postpartum weight retention [23, 24]. Postpartum weight retention is critical, not only negatively impacting returning to pregravid fitness levels, but the increased body mass index also places the mother and fetus at higher risk for negative health outcomes in subsequent pregnancies [6, 7, 25]. Furthermore, postpartum weight retention is associated with long-term maternal overweight/obesity [26-28] and increased waist circumference [29].

Clearly, gestational weight gain and postpartum weight retention are important factors in maternal and child health as well as military readiness; however, little is known about gestational weight gain and postpartum weight retention among TRICARE beneficiaries.

### 3.6. Research Design and Methods:

We will implement a stepped-care GWG intervention and a PPWL intervention for women with TRICARE benefits, while accommodating the unique military lifestyle and environment. We will randomize 450 participants to 1 of 3 arms: a) a gestational weight gain intervention (GWG-only); b) a postpartum weight loss intervention (PPWL-only), or c) a combined gestational weight gain and postpartum weight loss intervention (GWG+PPWL) in order to determine the efficacy of the interventions on GWG as well as PPWL. This design will allow the PPWL-only arm to be the comparison group for GWG (at the final pregnancy follow-up visit); the GWG-only arm to be the comparison group for PPWL (at 6-months and 12-months follow-up) and the GWG+PPWL arm to determine the additive or synergistic effects. Study measures will be obtained at screening, baseline, gestational week 32 and 36, and 6-weeks, 6-months, and 12-months postpartum and will include weight, height, maternal and infant medical outcomes, health care utilization, fitness test scores, waist circumference, self-reported exercise behaviors and nausea symptoms, accelerometry, feeding practices, demographics and program satisfaction. Process measures (e.g., session participation, self-monitoring) will be collected throughout the trial.

No inducements, monetary or otherwise, will be offered to terminate a pregnancy. Individuals engaged in the research will have no part in any decisions as to the timing, method, or procedures used to terminate a pregnancy and individuals engaged in the research will have no part in determining the viability of a neonate (45 CFR 46.204).

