#### 3.6.1. Interventions, Observations, or Data Sought:

**Procedure:** Interested individuals will be directed from our recruitment materials (e.g., posters, flyers, business cards, listservs, and electronic media) to visit the study recruitment office (located in the obstetric clinics) to learn more and determine whether they meet the eligibility criteria. If, after learning more about the study, individuals continue to be interested, written informed consent will be obtained and measures will be administered. The potential participant will also be asked to complete a one-week dietary and exercise self-monitoring run-in, turn in a copy of their fitness scores to study staff (if active duty), and receive medical clearance from their obstetrician to participate. (Note: In the unfortunate event that a potential participant miscarries before being randomized, she will have the opportunity to re-screen if she chooses.) Should she continue to be interested, she will return for a Baseline Visit and will be randomized to 1 of 3 conditions: a) GWG-only; b) PPWL-only; or c) GWG+PPWL and oriented to the assigned treatment condition.

**Randomization:** Participants (n=450) will be randomly allocated to 1 of the 3 conditions, using a computer algorithm under the direction of the study biostatistician, [name], with a sequence blocked by screening BMI category (i.e., normal weight, overweight, obese) in order to ensure equal distribution by condition with respect to BMI category. Each condition will have the same number of subjects.

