**Intervention Overview:** The novel stepped-care behavioral GWG and/or PPWL intervention--designed to assist participants meet the Institute of Medicine (IOM)-recommended GWG guidelines and produce PPWL--will be based on the Look AHEAD Intensive Lifestyle Intervention. The Look AHEAD Intensive Lifestyle Intervention methods are consistent with those utilized in previous studies of effective approaches to producing appropriate GWG and PPWL. However, the Look AHEAD approach offers greater structure and support than some of the methods used in previous work. We will also tailor our intervention to the military lifestyle (e.g., managing stressors such as increases in dietary intake, reduced physical activity related to spouse deployment, environmental facilitators such as access to the free fitness centers). We have previously tailored our interventions to the military lifestyle and environment, and our programs have been extremely well received by military personnel.

**GWG Intervention:** The GWG intervention will begin upon randomization to the GWG-only or the GWG+PPWL arm, and continue until the birth of the participant’s child. This intervention will provide individual, telephone-based sessions (20-30 minutes each), as detailed in Table 1, by trained interventionists. The number of possible telephone sessions will depend on the gestational age at randomization and the level of support needed by the participant to meet the IOM guidelines. The intervention will focus on self-monitoring, clear goals (i.e., GWG, caloric intake exercise), and problem solving.

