**PPWL Intervention:** The PPWL intervention will begin at 6-weeks postpartum (when most women will be approved for weight loss and exercise by their obstetrician) for those participants randomized to the PPWL-only or the GWG+PPWL arms, and will continue until 12-months postpartum. The PPWL intervention will provide at least monthly individual, telephone-based sessions (20-30 minutes each), as detailed in Table 2, by trained interventionists. (The number of possible telephone sessions will depend on the level of support needed by each participant to meet her weight loss goals). Similar to the GWG intervention, the PPWL intervention will focus on self-monitoring; weight, dietary intake and exercise goals; and problem solving.

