**Table 2. Stepped-Care Postpartum Weight Loss Intervention**

	Step 1	Step 2	Step 3
Trigger to Increase Intervention Intensity	<0.5-1 lb of weight loss per week at any monthly session	<0.5-1 lb of weight loss per week for 2 consecutive biweekly sessions	N/A
Contact Frequency	-Monthly 20-30 minute telephone sessions	-Biweekly 20-30 minute telephone sessions	-Weekly 20-30 minute telephone sessions -Weekly emailed materials
Dietary Recommendations	500 calorie deficit, tailored to breastfeeding status	Same as Step 1 with portion size measuring and daily dietary intake monitoring	↓ by 100-200 calorie per day until recommended weight loss achieved
Exercise	-↑ exercise to pregravid levels -Fitness tracker	-↑ exercise to pregravid levels -Fitness tracker	-↑ exercise to pregravid levels -Fitness tracker
Behavioral Strategies	-Weekly self monitoring of weight -Weekly emailed graph	-Daily self monitoring of weight, daily food intake & exercise -Weekly emailed graph -Goal setting and problem solving	-Daily self monitoring of weight, daily food intake & exercise -Weekly emailed graph -Goal setting & problem solving -Meal replacements & structured meal plans - Adapted Look AHEAD ILI materials -Toolbox resources
Trigger to Reduce Intervention Intensity	N/A	Return to weight loss within recommended range	Return to weight loss within recommended range

Failure to lose weight based on the expected trajectory (i.e., 1 lb per week until returning to their pregravid weight (for women who are in any pregravid weight category) or until they have achieved a 5% weight loss (for overweight and obese women, if they desire)) will trigger an increase in the intervention intensity (i.e., moving to the next step). That is, failure to lose weight based on the expected trajectory at any monthly session for those in Step 1 will trigger an increase in the intervention intensity (i.e., moving to Step 2) and any participant in Step 2 who is losing less than the expected trajectory for two consecutive biweekly sessions will trigger an increase in the intervention intensity (i.e., move to Step 3).

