**Weight goals:** Weight loss from birth to 6-weeks postpartum is fairly standard—approximately 6 kilograms (or 13 pounds)—regardless of pregravid weight category and GWG [29]. For women with a normal pregravid BMI, the PPWL goal (initiated at 6-weeks postpartum) will be to return to the pregravid weight. For women who were overweight or obese pre-pregnancy, the PPWL goal (initiated at 6-weeks postpartum) will be to at least return to their pregravid weight and, if desired, lose up to an additional 5% of their pregravid weight. All participants will be advised to lose weight at a rate of approximately 1 pound per week, which has been shown to not have adverse effects on infant growth or breast milk production. All women will be given a tailored graph indicating the recommended PPWL trajectory. They will be prompted to weigh themselves at least weekly on the electronic scale provided at baseline (which will upload the weight automatically to a secure website). The electronic scale will be issued to the subject as part of treatment on a hand receipt. Due to depreciation of the scale over 21 months of use during the study, the scales would be valued at near zero, and therefore subjects will not be required to return them. The electronic scales are part of the treatment and not considered a form of compensation for participating in the study. These weights will be plotted on a graph and emailed to them weekly along

with personalized feedback from their interventionist about their weight trajectory. The graph will clearly identify weight losses that are both greater than recommended and below recommendations. Participants who are losing weight faster than expected will be instructed to increase their caloric intake and to monitor their weight daily. Participants who lose more weight than expected at 2 consecutive monthly intervention sessions will be referred to their obstetrician for guidance, but will be retained in the study.

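### For postpartum weight the three arms cannot establish additivity or synergy, and the added-benefit contrast they can give (GWG added to PPWL) is not named

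*Combined protocol and SAP*

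**What the plan says.** Section 3.6 assigns each arm a role. PPWL-only is the comparator for gestational weight gain, GWG-only is the comparator for postpartum weight loss at 6 and 12 months, and the third role is "the GWG+PPWL arm to determine the additive or synergistic effects". Neither adjective is defined.

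Section 3.6.1 states that each participant "will be randomized to 1 of 3 conditions: a) GWG-only; b) PPWL-only; or c) GWG+PPWL", using a sequence generated "with a sequence blocked by screening BMI category". No arm receives neither intervention.

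Hypothesis 2 (section 3.2) reads: "Participants randomized to the GWG+PPWL and PPWL-only arms will lose significantly more weight postpartum than those randomized to the GWG-only arm". It sets GWG+PPWL and PPWL-only each against GWG-only. GWG+PPWL against PPWL-only appears only in Hypothesis 1, and there for weight gain in pregnancy.

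The GWG intervention ends at birth. Section 3.6.1 then says "The PPWL intervention will begin at 6-weeks postpartum".

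Section 6.0 plans to analyze weight change from baseline through all visits. Section 6.1 sets the primary postpartum outcome as loss between 6 weeks and 12 months, compared across the three arms. Section 6.3 models the three arms by ANCOVA-type regression and, for Hypothesis 2, also adjusts for weight at 6 weeks postpartum. It specifies no interaction term and no pairwise contrast for the combined arm.

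**The concern.** Additivity and synergy are statements about whether two effects sum. Each effect is measured from a state without treatment, and after 6 weeks postpartum this trial has no such state. In that strict sense the combined arm cannot play the role that section 3.6 gives it.

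The looser sense, added benefit, has two halves, and the plan names only one. The missing half asks whether a pregnancy programme still matters at 12 months for women who will receive the postpartum programme anyway. That question bears on section 4 (Brief Summary), which foresees wide dissemination of one intervention or both.

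An analyst who took this contrast from the specified postpartum model would answer a narrower question. The outcome starts from a weight measured after randomization that the GWG intervention may have changed. The protocol makes this pathway plausible: section 3.5 treats excess gain as a predictor of later retention, and the PPWL weight goals in section 3.6.1 take loss from birth to 6 weeks as about 6 kg whatever the gestational gain.

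**Working it through.** **1. Estimability.** Let G and P indicate receipt of GWG and PPWL. Write the mean postpartum weight outcome as b0 + bG·G + bP·P + bGP·G·P. The rows (1, G, P, G×P) for the three arms are:

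- GWG-only: (1, 1, 0, 0)
- PPWL-only: (1, 0, 1, 0)
- GWG+PPWL: (1, 1, 1, 1)

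The rank is 3 for four parameters. A contrast is estimable only if appending its row leaves the rank unchanged.

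| Contrast | Row | Rank after appending | Estimable |
|---|---|---|---|
| Interaction (additivity or synergy) | (0, 0, 0, 1) | 4 | No |
| GWG+PPWL minus GWG-only | (0, 0, 1, 1) | 3 | Yes (Hypothesis 2) |
| PPWL-only minus GWG-only | (0, −1, 1, 0) | 3 | Yes (Hypothesis 2) |
| GWG+PPWL minus PPWL-only | (0, 1, 0, 1) | 3 | Yes (not named after delivery) |

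Moving the parameters along (1, −1, −1, 1) leaves all three arm means unchanged and shifts the interaction, so no model or sample size resolves it.

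Illustration with invented means: GWG-only 1, PPWL-only 3, combined 4. Interaction = 4 − 1 − 3 + neither = neither. Unobserved means of −1, 0, 1 and 2 give interactions of −1, 0, +1 and +2. The same data fit antagonism, additivity and synergy.

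In pregnancy PPWL has not yet started, so there is no interaction to test. The point is confined to postpartum weight.

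**2. What the 6-week reference does.** Let W0, W6 and W12 be weight at baseline, 6 weeks and 12 months:

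W12 − W0 = (W6 − W0) + (W12 − W6).

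For GWG+PPWL versus PPWL-only, let T be the effect on W12 − W0 and d the effect on W6 − W0. The unadjusted change from 6 weeks estimates T − d. In a linear model adjusted for 6-week weight, the arm coefficient is T − β·d, where β is the slope of 12-month on 6-week weight. Neither equals T in general. The documents give neither d nor β, so the gap cannot be sized.

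**3. Which comparisons this touches.**

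- GWG+PPWL versus PPWL-only: the arms differ in GWG exposure before 6 weeks, so d may be non-zero.
- PPWL-only versus GWG-only (Hypothesis 2): the arms also differ in GWG exposure, so this comparison too is conditioned on a post-randomization weight.
- GWG+PPWL versus GWG-only (Hypothesis 2): both arms receive GWG and PPWL starts only at 6 weeks, so the concern does not arise in the same way.

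**4. Precision of the proposed contrast.** Section 6.2 plans 755 enrolled and 450 completing: 3 × 150 = 450. It states no alpha, power, effect size or SD, so there is no power figure to reproduce. Assuming two-sided 5% and 80% power, with n = 150 per arm:

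- SE = SD × √(2/150) = 0.115 SD
- 95% CI half-width = 1.960 × 0.1155 = 0.23 SD
- Detectable difference = (1.960 + 0.842) × 0.1155 = 0.32 SD

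**The case against.** The strongest reply is that the two adjectives appear once, undefined, in a design overview. No hypothesis, outcome or model claims an interaction, and on the ordinary reading of added benefit three arms are enough. A three-level arm factor yields GWG+PPWL versus PPWL-only directly, and section 6.0 already covers change from baseline. Section 6.3 also ties the 6-week adjustment to Hypothesis 2, so it is not clearly required for a contrast outside that hypothesis.

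Much of this stands. The contrast is available in the plan and lacks only a name, and no planned test fails. But the loose reading does not close the gap. With or without adjustment, the only specified postpartum outcome starts at 6 weeks, so the three-arm comparison of that outcome does not give the total effect of adding GWG.

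A reader might infer that the 6-week reference hides a material benefit. The documents do not show that. Both compared arms receive PPWL. For women of normal pregravid BMI, "the PPWL goal (initiated at 6-weeks postpartum) will be to return to the pregravid weight"; overweight and obese women have at least that goal. "Failure to lose weight based on the expected trajectory" raises intensity, so the part removed could be near zero. An effect not carried through 6-week weight, for example through skills learned in pregnancy, would still show: "The intervention will focus on self-monitoring, clear goals (i.e., GWG, caloric intake exercise), and problem solving".

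A reader might also apply the fall from 755 to 450 to the 450 randomized and conclude that precision is worse than shown. Sections 6.2 and 6.4 give 450 as completers, so that would count the loss twice.

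**Conclusion.** The concern holds as a minor gap in wording and pre-specification. The non-estimability of strict additivity or synergy for postpartum weight follows from the arm structure alone and needs no numerical assumption. That GWG added to PPWL is unnamed after delivery, and that the specified outcome does not estimate its total effect, follows from sections 3.2, 6.1 and 6.3. No size is claimed for what the 6-week reference removes. The precision figures rest on 150 completers per arm and on the assumed alpha and power.

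Two stronger conclusions are tempting. One is that the missing cell undermines the trial's hypotheses. It does not: neither Hypothesis 1 nor Hypothesis 2 uses that cell. The opposite is that Hypothesis 2 is untouched by everything here. That is too broad, because its PPWL-only versus GWG-only comparison shares the 6-week reference problem.

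**What to change.** In section 3.6, replace the clause on the role of the combined arm with: *to estimate the incremental effects of adding PPWL to GWG (Hypothesis 2) and of adding GWG to PPWL*.

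In section 6.3, name one secondary contrast: GWG+PPWL versus PPWL-only on 12-month minus baseline weight, adjusted for baseline weight and screening BMI category (the blocking factor) and not for 6-week weight, reported with a 95% confidence interval. Baseline is preferred as the reference because staff measure it, whereas section 3.6.8 obtains pregravid weight by self-report. The primary outcomes and Hypotheses 1 and 2 can stay as written.

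The cost is wording in two sections and one estimate on weights already collected. No arm, visit or participant is added; a fourth arm would be needed only to keep the strict synergy claim. The downside is one more secondary estimate that leaves effects well below about 0.32 SD uncertain, and the loss of a synergy claim that the design could not support.
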